16.4. Appendix 4: Study Phases and Treatment Emergent Adverse Events

16.4.1. Study Phases

Study Phase	Definition
Pre-Treatment	Date ≤ Study Treatment Start Date
On-Treatment	Study Treatment Start Date < Date

Some datasets include the first dosing day as On-Treatment and some exclude the first dosing date as On-Treatment. The first dosing day (Day 1) is considered Pre-Treatment for ECOG, ECG, vital signs, liver events, lab tests, cardiac scan, and other safety domains. The first dosing day (Day 1) is considered to be On-Treatment for adverse events and concomitant medications.

16.4.1.1. Study Time Periods for Concomitant Medications and Blood and Blood Supportive Care Products

Concomitant Medication and Blood and Blood Supportive Care Product start and end dates will be assigned to study time periods in relation to first dose of study treatment as defined below. The start date references time flag variables and end date reference time flag variables will be added to the concomitant medications and blood and blood supportive products datasets, respectively.

- **Start relative to treatment:** Assign to 'BEFORE' if start date is prior to study treatment start date or if subject has not taken any study treatment or (start date is missing and end date is before study treatment start date). Else assign to 'DURING' if the start date falls into the on-therapy period as defined above or if subject is ongoing (not all study treatment discontinuation records completed) or start date is missing. Else assign to 'AFTER' if start date is after the on-therapy period.
- **End relative to treatment:** Assign to 'BEFORE' if end date is prior to study treatment start date or if subject has not taken any study treatment. Else assign to 'DURING' if start date falls into the on-therapy period or if subject is ongoing (not all study treatment discontinuation records completed) or (end date is missing and start relative to treatment not 'AFTER'). Else assign to 'AFTER' if start date is after the on-therapy period or (end date is missing and start relative to treatment='AFTER').

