Only on-therapy blood and blood supportive care products that start after the start of study treatment are included in the Blood Products and Blood Supportive Care Product summaries. Therefore, for summary tables, include blood and blood supportive care product records where start relative to treatment in ('DURING') and end relative to treatment in ('DURING','AFTER'). All data will be reported in listings.

Concomitant medication start relative to treatment and end relative to treatment flags are used to select data to include in the Concomitant Medication summaries as follows:

- **Summary of Concomitant Medications:** This summary will contain medications including those with start date prior to study treatment start date and continue

(missing end date or end date after study treatment start date) on therapy. Note that any medications with start date and end date prior to study treatment start date will be excluded. In addition, any medication that was started during post-therapy will be excluded. Include concomitant medication records where start relative to treatment in ('BEFORE','DURING') and end relative to treatment in ('DURING','AFTER').

- Summary of Concomitant Medications with On-Therapy Onset: This summary will contain medications with start date after study treatment start date. In addition, any medication that was started during post-therapy (see above for definition of post-therapy) will be excluded. Include concomitant medication records where start relative to treatment in ('DURING') and end relative to treatment in ('DURING','AFTER').

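### The end-of-medication flag tests the start date, so medications begun before treatment and stopped on or after the first dose drop out of the concomitant medication summary

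*SAP*

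**What the plan says.** Section 16.4.1.1 assigns every concomitant medication and blood product record two flags, one for its start and one for its end relative to study treatment. The end flag has three branches, taken in order:

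- BEFORE: "Assign to 'BEFORE' if end date is prior to study treatment start date or if subject has not taken any study treatment".
- DURING: "Else assign to 'DURING' if start date falls into the on-therapy period or if subject is ongoing", or when "end date is missing and start relative to treatment not 'AFTER".
- AFTER: "Else assign to 'AFTER' if start date is after the on-therapy period or (end date is missing and start relative to treatment='AFTER".

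For concomitant medications the first dosing day counts as on therapy: "The first dosing day (Day 1) is considered to be On-Treatment for adverse events and concomitant medications".

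The summary then selects on both flags: "Include concomitant medication records where start relative to treatment in ('BEFORE','DURING') and end relative to treatment in ('DURING','AFTER". The prose introducing that rule states the purpose: "This summary will contain medications including those with start date prior to study treatment start date and continue" on therapy. It adds in parentheses that continuing means either a missing end date or an end date after the start of treatment. Section 6.6 defines a concomitant medication more simply, as one taken at any point in the on-therapy window.

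**The concern.** Only the BEFORE branch of the end flag uses the end date. The DURING and AFTER branches repeat the criterion of the start flag, so the variable does not describe when the medication ended. The branches also fail to cover all cases: a medication that started before treatment and has a recorded end on or after first dose satisfies none of them.

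Because the selection rule needs an end flag of DURING or AFTER, a blank flag excludes the record. The loss would be systematic. Baseline medications with no recorded stop date stay in the table, while those recorded as stopped on or after first dose leave it. A programmer who follows the algorithm and one who follows the prose would produce different tables from the same plan.

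**Working it through.** The plan gives no figure to reproduce here; the check is one of logic. I applied the start flag, the end flag and the selection rule literally to combinations of dates, then repeated this with the end date tested in the DURING and AFTER branches.

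**Inputs**

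- Flag definitions, Day 1 convention and selection rule: Section 16.4.1.1 and the study phase table in Section 16.4.1.
- The study phase table gives the on-treatment phase no upper limit. I ran the check that way and again with an assumed upper limit of 100 days after first dose.
- Start date: missing, 10 days before first dose, day of first dose, 20 days after, 130 days after.
- End date: missing, 5 days before first dose, day of first dose, 30 days after, 150 days after.
- Subject: treatment discontinued, or still ongoing.

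**One record followed through.** The subject is discontinued, the medication started 10 days before first dose and ended 30 days after.

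1. The start flag is BEFORE, because the start precedes treatment.
2. The end flag is not BEFORE, because the end is later than the start of treatment.
3. It is not DURING, because the start is not on therapy, the subject is not ongoing and the end date is not missing.
4. It is not AFTER, because the start is not after the on-therapy period and the end date is not missing.
5. The end flag is blank. The summary requires "end relative to treatment in ('DURING','AFTER"), so the record is excluded. The prose includes it.

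**All combinations whose inclusion changes (discontinued subjects)**

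| Start | End | Start flag | End flag as written | In summary as written | End flag using end date | In summary after the change |
|---|---|---|---|---|---|---|
| 10 days before | day of first dose | BEFORE | blank | no | DURING | yes |
| 10 days before | 30 days after | BEFORE | blank | no | DURING | yes |
| 10 days before | 150 days after | BEFORE | blank | no | DURING (AFTER with the 100-day limit) | yes |
| missing | day of first dose | DURING | blank | no | DURING | yes |
| missing | 30 days after | DURING | blank | no | DURING | yes |
| missing | 150 days after | DURING | blank | no | DURING (AFTER with the 100-day limit) | yes |

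The same six rows fail with or without the upper limit. No other combination changes its inclusion. Two conditions rescue records as written: a missing end date and a subject still ongoing both give DURING.

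**How much the rescues cover.** Section 3.3 places the final analysis after all participants have completed the study, so the ongoing condition should rarely apply. Section 16.7.2.1 imputes partial stop dates for concomitant medications, so a partial end date, once imputed, no longer counts as missing.

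**Tables reached.** The pre-treatment-start case affects the Summary of Concomitant Medications, Tables 1.0210 to 1.0213. It cannot affect the on-therapy-onset or blood product summaries, because those require a start flag of DURING. The missing-start case does reach them, since they use the same end-flag condition.

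**The case against.** The strongest reply is that the intent is plain. The section says end dates are to be assigned to periods, its prose includes medications that continue past the start of treatment, and Section 6.6 agrees. The bullet looks like wording carried over from the start flag, and a blank flag may well be noticed in programming. That is fair as to cause, and it makes the harm conditional on literal coding. It does not remove the contradiction, because the bullet is the operative specification.

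Other points limit the size:

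- The tables are descriptive. No efficacy result depends on this flag, and concomitant medications are also listed separately.
- Section 6.6 counts each subject once per ingredient. A subject who also has an on-therapy record for the same ingredient is still counted, so lost records are not the same as lost subject counts.
- The prose speaks of an end date after treatment start and is silent on an end on Day 1 itself. That case rests on Section 6.6 together with the Day 1 convention.
- While the on-treatment phase has no upper limit, changing the AFTER branch has no effect; the change to DURING restores the records.

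All four stand as qualifications. None shows that the rule as written gives the intended table.

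**Conclusion.** The concern holds: the end flag is wrong as written. In discontinued subjects, every medication begun before first dose with a recorded stop on or after first dose is excluded from the concomitant medication summary, against the plan's own description of that summary. Records with a missing start date and a known end on or after first dose are excluded too, and this smaller gap extends to the on-therapy-onset and blood product summaries.

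The number of subjects and ingredients affected cannot be stated from the document. The conclusion assumes that the bullet is programmed literally and that, at the final analysis, few subjects are still flagged as ongoing. It does not depend on whether the on-therapy period has an upper limit. Because only descriptive displays are touched, this should be corrected but does not threaten the main conclusions of the study.

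**What to change.** In the end-flag bullet of Section 16.4.1.1, test the end date instead of the start date in both the DURING and the AFTER conditions, leaving the ongoing-subject and missing-end clauses as they are. In the check above this restored all six lost combinations and altered the inclusion of no other record. For the AFTER category to have any content, the section also needs to state when the on-therapy period ends; its reference to an earlier definition of post-therapy points to nothing in the text. The cost of the main change is two substitutions in the SAP and a re-run of the flag derivation and the tables that use it. No new data are needed.

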16.4.2. Treatment Emergent Flag for Adverse Events

Flag	Definition
Treatment Emergent	
 • Study Treatment Start Date \leq AE Start Date • AE Start Date is missing

NOTES:

- If the study treatment stop date is missing, then the AE will be considered to be On-Treatment.
- Time of study treatment dosing and start/stop time of AEs should be considered, if collected.

16.5. Appendix 5: Data Display Standards & Handling Conventions

16.5.1. Reporting Process

Software	

 The currently supported versions of SAS software will be used. 	
Reporting Area	
HARP Server	: US1SALX00259
HARP Compound	: arprod\gsk2859716\bma117159\
Analysis Datasets	

 Analysis datasets will be created according to CDISC standards (SDTM IG Version 3.1.3 & ADaM IG Version 1.0). 	
Generation of RTF Files	

 RTF files will be generated for all tables. 	

16.5.2. Reporting Standards

General	

 The current GSK Integrated Data Standards Library (IDSL) will be applied for reporting, unless otherwise stated (IDSL Standards Location: https://spope.gsk.com/sites/IDSLLibrary/SitePages/Home.aspx): 
 4.03 to 4.23: General Principles 5.01 to 5.08: Principles Related to Data Listings 6.01 to 6.11: Principles Related to Summary Tables 7.01 to 7.13: Principles Related to Graphics Do not include subject level listings in the main body of the GSK Clinical Study Report. All subject level listings should be located in the modular appendices as ICH or non-ICH listings 	
Formats	

 GSK IDSL Statistical Principles (5.03 & 6.06.3) for decimal places (DP's) will be adopted for reporting of data based on the raw data collected, unless otherwise stated. Numeric data will be reported at the precision collected on the eCRF. The reported precision from non eCRF sources will follow the IDSL statistical principles but may be adjusted to a clinically interpretable number of DP's. 	
Planned and Actual Time	

 Reporting for tables, figures and formal statistical analyses: 
 Planned time relative to dosing will be used in figures, summaries, statistical analyses and calculation of any derived parameters, unless otherwise stated. The impact of any major deviation from the planned assessment times and/or scheduled visit days on the analyses and interpretation of the results will be assessed as appropriate. Reporting for Data Listings: 
 Planned and actual time relative to study drug dosing will be shown in listings (Refer to IDSL Statistical Principle 5.05.1). Unscheduled or unplanned readings will be presented within the subject's listings. 	

Unscheduled Visits	

 Unscheduled visits will not be included in summary tables and/or figures. For by planned time analysis, unscheduled visits will not be included; For worst-case analysis, unscheduled visits will be included. All unscheduled visits will be included in listings. 	
Descriptive Summary Statistics	
Continuous Data	Refer to IDSL Statistical Principle 6.06.1
Categorical Data	N, n, frequency, %
Graphical Displays	

 Refer to IDSL Statistical Principals 7.01 to 7.13. 	

16.5.3. Reporting Standards for Pharmacokinetic

Pharmacokinetic Concentration Data	
PC Windows Non-Linear (WNL) File	PC WNL file (CSV format) for the non compartmental analysis by Clinical Pharmacology Modelling and Simulation function will be created according to [Insert document name]. Note: Concentration values will be imputed as per GUI_51487
Descriptive Summary Statistics, Graphical Displays and Listings	Refer to IDSL PK Display Standards. Refer to IDSL Statistical Principle 6.06.1. Note: Concentration values will be imputed as per GUI_51487 for descriptive summary statistics/analysis and summarized graphical displays only.
NONMEM/Pop PK File	Pop-PK file (CSV format) for the POP-PK analysis by Clinical Pharmacology Modelling and Simulation function will be created according to the data specification detailed in Section 16.9.1 Population Pharmacokinetic (PopPK) Dataset Specification.
NONMEM/PK/PD File	PK/PD file (CSV format) for the PK/PD analysis by Clinical Pharmacology Modelling and Simulation function will be created according to the data specification detailed in Section 16.10.1 Pharmacokinetic/Pharmacodynamic Dataset Specification.
Pharmacokinetic Parameter Derivation	
PK Parameter to be Derived by Programmer	The following PK parameters will be derived by the Programmer:
Pharmacokinetic Parameter Data	
Is NQ impacted PK Parameters Rule Being Followed	Yes, refer to [Standards for Handling NQ Impacted PK Parameters].
Descriptive Summary Statistics, Graphical Displays and Listings	Refer to IDSL PK Display Standards.

16.5.4. Extended Loss to Follow-up or Extended Time without an Adequate Assessment

For subjects, if two or more scheduled disease assessments are missed and are then followed by an assessment of PD or death, PFS will be censored at the last adequate assessment prior to PD or death. When the scheduled disease assessment is every 3 weeks, a window of 49 days (6 weeks + 7 day window) will be used to determine whether there was an extended time without adequate assessment. That is, if the time difference between PD/death and last adequate assessment is more than 49 days, then PFS will be censored at the last adequate assessment prior to PD/death.

16.5.5. Date Associated with Response

Investigator assessment of disease is entered in the eCRF on the VISIT form. The date of the VISIT is captured but the date of the response assessment is not captured separately. The date associated with response will be the visit date for the VISIT on which the investigator assessed disease. A disease assessment may occur at an unscheduled visit. The date of the unscheduled visit would be assigned to any response assessed on that date. In the following section, unless otherwise specified, the disease assessment denotes post-baseline assessment.

16.6. Appendix 6: Derived and Transformed Data

16.6.1. General

Multiple Measurements at One Analysis Time Point

 • Mean of the measurements will be calculated and used in any derivation of summary statistics but if listed, all data will be presented. • Participants having both High and Low values for Normal Ranges at any post-baseline visit for safety parameters will be counted in both the High and Low categories of Any visit post-baseline row of related summary tables. This will also be applicable to relevant Potential Clinical Importance summary tables.
Study Day

 • Calculated as the number of days from First Dose Date: 
 • Ref Date = Missing → Study Day = Missing • Ref Date < First Dose Date → Study Day = Ref Date - First Dose Date • Ref Date ≥ First Dose Date → Study Day = Ref Date - (First Dose Date) + 1

16.6.2. Study Population

Extent of Exposure

 • Number of days of exposure to study drug will be calculated based on the formula: Duration of Exposure in Days = Treatment Stop Date - (Treatment Start Date) + 1 • Participants who were randomized but did not report a treatment start date will be categorised as having zero days of exposure. • The cumulative dose will be based on the formula: Cumulative Dose = Sum of Dose at Each Cycle • Dose intensity per cycle will be based on the formula: Dose intensity Per Cycle = Cumulative Dose / Total Number of Cycles

16.6.3. Efficacy

Laboratory Parameters
Serum M-protein, Urine M-protein, Serum FLC

 • If a laboratory value which is expected to have a numeric value for summary purposes, has a non-detectable level reported in the database, where the numeric value is missing, but typically a character value starting with '<x' or '>x' (or indicated as less than x or greater than x in the comment field) is present, the number of significant digits in the observed values will be used to determine how much to add or subtract in order to impute the corresponding numeric value. 
 ○ Example 1: 2 Significant Digits = '< x' becomes x - 0.01 ○ Example 2: 1 Significant Digit = '> x' becomes x + 0.1 ○ Example 3: 0 Significant Digits = '< x' becomes x - 1

16.6.4. Safety

Adverse Events
AE'S OF Interest

• Corneal events• Thrombocytopenia• Neutropenia• Hematologic Toxicity• Infusion-related Reactions as collected in the eCRF

16.7. Appendix 7: Reporting Standards for Missing Data

16.7.1. Premature Withdrawals

Element	Reporting Detail
General	
 • Subject study completion (i.e. as specified in the protocol) was defined as: 
 ○ For Part 1 (dose-escalation phase), a completed subject is one who has completed at least 1 cycle of study treatment and an End of Study Visit without events causing them to withdraw or discontinue from the study for reasons listed in Section 6.3 of the protocol. ○ For Part 2 (expansion cohort), a completed subject is one who has received at least one dose of study treatment without events causing them to withdraw or discontinue study treatment for reasons listed in Section 6.3 of the protocol and completed an End of Study Visit. ○ A participant will be considered to have completed the study if he or she has received at least one dose of the study treatment and, has died before the end of the study, has not been lost to follow-up, or has not withdrawn consent from study participation. • Withdrawn subjects may be replaced in the study. • All available data from participants who were withdrawn from the study will be listed and all available planned data will be included in summary tables and figures, unless otherwise specified.

16.7.2. Handling of Missing Data

Element	Reporting Detail
General	
 • Missing data occurs when any requested data is not provided, leading to blank fields on the collection instrument: 
 ○ These data will be indicated by the use of a blank in subject listing displays. Unless all data for a specific visit are missing in which case the data is excluded from the table. ○ Answers such as “Not applicable” and “Not evaluable” are not considered to be missing data and should be displayed as such.
Outliers	
 • Any participants excluded from the summaries and/or statistical analyses will be documented along with the reason for exclusion in the clinical study report.
Responder Analysis	
 • For endpoints which determine the percentage of responders, subjects with unknown/not evaluable or missing best overall response will be assumed to be non-responders, and will be included in the denominator when calculating the percentages.
Time to Event	
 • Because study treatment is dependent on the study endpoints (e.g., progression, i.e. not a fixed treatment duration), the length of treatment for each subject will depend on the efficacy and toxicity of the treatment, so the duration of treatment will vary across subjects. Similarly the duration of follow up will also vary. All available time-to-event data will be analyzed using suitable statistical methods; subjects with shorter treatment and follow-up due to the natural history of their disease or medical necessities of the treatment of their disease will not be considered to have missing time-to-event data.

16.7.2.1. Handling of Missing and Partial Dates

Element	Reporting Detail
General	
 • Partial dates will be displayed as captured in subject listing displays. • Imputed partial dates will not be used to derive study day, duration (e.g. duration of adverse events), or elapsed time variables. In addition, imputed dates are not used for deriving the last contact date in the overall survival analysis dataset. The imputed AE dates will only to be used in the figures “Profile Plot for Patients with No Corneal Event or Grade 1 Corneal Event” and “Profile Plot for Patients with Grade 2 or Higher Corneal Events”. • Imputed dates will not be displayed in listings. However, where necessary, display macros may impute dates as temporary variables for the purpose of sorting data in listings only. In addition, partial dates may be imputed for ‘slotting’ data to study time periods or for specific analysis purposes as outlined below.
Adverse Events	
 • The eCRF allows for the possibility of partial dates (i.e., only month and year) to be recorded for AE start and end dates; that is, the day of the month may be missing. 
 ○ The eCRF allows for the possibility of partial dates (i.e., only month and year) to be recorded for AE start and end dates; that is, the day of the month may be missing. 
 ○ Missing Start Day: First of the month will be used unless this is before the start date of study treatment; in this case the study treatment start date will be used and hence the event is considered On-treatment as per Appendix 4: Study Phases and Treatment Emergent Adverse Events. ○ Missing Stop Day: Last day of the month will be used, unless this is after the stop date of study treatment; in this case the study treatment stop date will be used. • Completely missing start or end dates will remain missing, with no imputation applied. Consequently, time to onset and duration of such events will be missing.
Concomitant Medications	
 • Partial dates for any concomitant medications recorded in the CRF will be imputed using the following convention: 
 ○ If the partial date is a start date, a '01' will be used for the day and 'Jan' will be used for the month ○ If the partial date is a stop date, a '28/29/30/31' will be used for the day (dependent on the month and year) and 'Dec' will be used for the month. • The recorded partial date will be displayed in listings.

Element	Reporting Detail
Anti-Cancer Therapy (Where applicable), Radiotherapy and Surgical Procedures for Time-to-Event Endpoint and Response	
 • Start dates for follow-up anti-cancer therapy, radiotherapy (where applicable), and surgical procedures (where applicable) will be temporarily imputed in order to define event and censoring rules for progression-free survival, response rate, time to progression, duration of response or time to response (i.e. start date for new anti-cancer therapy). The imputed dates will not be stored on the anti-cancer therapy, radiotherapy, or surgical procedure datasets. • If missing start day, month, and year, then no imputation for completely missing dates • If missing start day and month, then no imputation should be done • If missing start day, then do the following: • If partial date falls in the same month as the last dose of study treatment, then assign to earlier of (date of last dose of study treatment+1, last day of month). • If partial date falls in the same month as the subject's last assessment and the subject's last assessment is PD, then assign to earlier of (date of PD+1, last day of month). • If both rules above apply, then assign to latest of the 2 dates • Otherwise, impute missing day to the first of the month. • If missing end date, then no imputation should be done.

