33. Optional follow-up telephone interview to explore visual symptoms and changes in symptoms and related impacts following treatment discontinuation be performed at least 6 months following the End of Study Treatment visit. This interview would only be for those subjects who experienced corneal symptoms during treatment and consent to participate.
34. End of treatment visit should be performed within 30 days (+7 days) after the last dose or prior to the start of new anti-cancer treatment, whichever is earlier. In cases where more than 30 days (+7 days) have elapsed from the date of the subject's last dose due to dosing delays and a subsequent decision to take the subject off treatment, the end of study treatment visit should be scheduled as soon as possible to allow the final assessments to be performed at the earliest date.

35. Participants with corneal signs or symptoms at the end of study treatment visit should be monitored by ophthalmic exam once a month after the last study dose until deemed clinically stable by an eye care professional complete resolution or for 12 months (whichever comes first). Corneal exams to include BCVA and slit lamp examination (with special focus on cornea). Participants who have completed treatment or the 3 month follow up visit (end of study) will be re-consented for additional ophthalmology follow up.

Abbreviations:

ADA = Antibody Drug Antibody; ALP = alkaline phosphatase; BCVA = best corrected visual acuity; BNP = B-type natriuretic peptide; C1D1 = Cycle 1 Day 1, etc.; cfdNA = Circulating free DNA; CK = creatinine kinase; CRP = C-reactive protein; EM = extramedullary; EOI = End of Infusion; FLC = free light chain; PD = Pharmacodynamics; PK = Pharmacokinetics; QID = 4 times a day; SOI = start of infusion; SPEP = serum protein electrophoresis; UPEP = urine protein electrophoresis

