13.0160	All Treated	SAFE_F1	Proportions of Subjects with Infusion-related Reactions (Part 1)	Report for sub-population: Part 1. Pool all subjects together.	SAC [A]
13.0161	All Treated	SAFE_F1	Proportions of Subjects with Infusion-related Reactions (Part 2 MM)	Report for sub-population: Part 2 MM.	SAC [A]
ECG					
13.0200	All Treated	OECG4	Fridericia's QTc Shifts from Baseline to Worst-case Post Baseline (Part 1)	Report for sub-population: Part 1. Pool all subjects together. If machine read QTcF is missing, use the manual read QTcF and add footnote that Machine and Manual calculate values are	SAC [A]

Safety: Figures					
No.	Population	IDSL / Example Shell	Title	Programming Notes	Deliverable [Priority]
				collapsed together.	
13.0201	All Treated	OECG4	Fridericia's QTc Shifts from Baseline to Worst-case Post Baseline (Part 2 MM)	Report for sub-population: Part 2 MM. If machine read QTcF is missing, use the manual read QTcF, and add footnote that Machine and Manual calculate values are collapsed together	SAC [A]
13.0202	All Treated	OECG4	Fridericia's QTc Shifts from Baseline to Worst-case Post Baseline (Part 2 NHL)	Report for sub-population: Part 2 NHL. If machine read QTcF is missing, use the manual read QTcF, and add footnote that Machine and Manual calculate values are collapsed together	SAC
Patient Profile Plot					
13.0190	All Treated	SAFE_F2	Profile Plot for Patients with No Corneal Event or Grade 1 Corneal Event (Part 2 MM)	Report for sub-population: Part 2 MM.	SAC [A]
13.0191	All Treated	SAFE_F2	Profile Plot for Patients with Grade 2 or Higher Corneal Events (Part 2 MM)	Report for sub-population: Part 2 MM.	SAC [A]

NOTES:

A. Indicates which displays will be generated for the reporting effort for multiple myeloma

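### A partial AE stop date is cut back to the treatment stop date, so in the two corneal profile plots it can contradict the recorded month or precede onset

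*SAP*

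**What the plan says.** The adverse-event part of SAP Section 16.7.2.1 deals with AE dates that lack only the day. For stop dates: "Last day of the month will be used, unless this is after the stop date of study treatment"; when month-end is later, "in this case the study treatment stop date will be used". For start dates: "First of the month will be used unless this is before the start date of study treatment", in which case treatment start is used. The start rule has a floor at treatment start but no ceiling at treatment stop. Nothing requires an imputed stop to be on or after its start. Completely missing start or stop dates stay missing.

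The general part of the same section limits where these dates go. "Imputed partial dates will not be used to derive study day, duration (e.g. duration of adverse events), or elapsed time variables". Listings show partial dates as captured. For AEs, "The imputed AE dates will only to be used in the figures" that follow, and it names two: the profile plots for patients with no or Grade 1 corneal events and for patients with Grade 2 or higher events. In Section 16.12.9 these are Figures 13.0190 and 13.0191, both for Part 2 MM.

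Two other places bear on whether stop dates after treatment can occur. Section 16.4.1 defines the on-treatment phase as "Study Treatment Start Date < Date", with no upper limit, and Section 16.4.2 likewise sets no end to treatment emergence. Footnote 35 of the Part 2 MM schedule (Section 16.2.3.1) has patients with corneal signs or symptoms at the end of treatment "monitored by ophthalmic exam once a month after the last study dose", for up to 12 months.

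**The concern.** The rule applies where month and year are known. If the recorded month is later than the month treatment stopped, month-end is always after treatment stop, so the cap always applies and overwrites known information with a date the record excludes. That differs from choosing a conservative value within the range the record leaves open.

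The plan routes these dates only to displays of corneal events, which it expects may outlast treatment and which it follows monthly off drug. For stop months after the treatment-stop month, the error runs one way: the event is drawn as ending sooner than it did. The same corneal event would carry its recorded later month in Listing 1.0270 and an end at treatment stop in the figure.

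**Working it through.** No sample size or error rate is involved, so this is a logical check with date arithmetic.

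**Inputs from the SAP.** Stop-day rule, start-day rule and permitted uses: Section 16.7.2.1. Scope of AEs after the last dose: Sections 16.4.1 and 16.4.2. Corneal follow-up of up to 12 months: Section 16.2.3.1, footnote 35. Treatment stop date is taken as the last dose date, the natural reading of Sections 6.5 and 16.6.2.

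**Assumed for illustration, not from the SAP.** Last dose 10 March 2017, and the onset and stop months below.

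**Formulas.**
- SAP rule: imputed stop = min(last day of recorded month, treatment stop date).
- Earliest date the record allows = max(first day of recorded month, AE start date).
- Certain error = earliest allowed date − imputed stop, if positive.

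| Onset | Recorded stop | Imputed stop (SAP) | Earliest allowed | Certain error (days) | Month-end, no cap |
|---|---|---|---|---|---|
| 5 Jan 2017 | Feb 2017 | 28 Feb 2017 | 1 Feb 2017 | 0 | 28 Feb 2017 |
| 1 Feb 2017 | Mar 2017 | 10 Mar 2017 | 1 Mar 2017 | 0 | 31 Mar 2017 |
| 1 Feb 2017 | Jun 2017 | 10 Mar 2017 | 1 Jun 2017 | 83 | 30 Jun 2017 |
| 1 Feb 2017 | Sep 2017 | 10 Mar 2017 | 1 Sep 2017 | 175 | 30 Sep 2017 |
| 1 Feb 2017 | Mar 2018 | 10 Mar 2017 | 1 Mar 2018 | 356 | 31 Mar 2018 |
| 4 Apr 2017 | Apr 2017 | 10 Mar 2017 | 4 Apr 2017 | 25 | 30 Apr 2017 |
| 5 Apr 2017 | Jun 2017 | 10 Mar 2017 | 1 Jun 2017 | 83 | 30 Jun 2017 |

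For September: 21 days left in March + 30 + 31 + 30 + 31 + 31 + 1 = 175. If the event really ended on 30 September, the error is 175 + 29 = 204 days.

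**Reading the table.**
- Rows 1 and 2: where treatment stopped in or after the recorded month, the rule does no harm or gives a date that is still possible. In row 2 it merely picks an earlier date than month-end.
- Rows 3 to 5: the imputed date lies outside the recorded month. The certain error equals the interval from last dose to the start of that month. Row 5 shows the scale at the far end of the 12-month follow-up.
- Rows 6 and 7: the imputed stop falls 25 and 26 days before onset.
- Without the cap, the largest possible error is from the first to the last day of a 31-day month: 31 − 1 = 30 days.

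**The case against.** The strongest case on the other side is about reach, and most of it stands. The wording and the arithmetic are not in dispute.

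- **No estimate uses these dates.** They are barred from study day, AE duration and elapsed time, and from listings. The corneal onset and duration tables (3.0180 to 3.0183) and Listing 1.0270 are untouched. This stands.
- **Persistent events with no stop date are not cut back**, because completely missing dates stay missing. Only events with a recorded month and year but no day are affected. This stands.
- **Frequency is unknown.** Off-treatment follow-up is by monthly dated eye examination, so a full stop date may often be available. It also ends earlier than 12 months if the eye is judged stable or resolved, so the longest errors are a worst case. This stands.
- **The plot layout is not visible in the text available.** That AE end dates are drawn is inferred from the plan sending imputed AE dates there and nowhere else. If the time axis ended at treatment stop, the cap would only trim a bar at the edge. This stands as an assumption.

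A reader might infer that the plan misstates the reversibility of corneal toxicity in general. The document does not support that. Recovery is also reported from data this rule never touches: duration to resolution of the first corneal event, the visit-level visual acuity and corneal examination listings, and the follow-up OSDI and NEI-VFQ-25 listings.

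None of this makes the rule right where it applies. The concomitant-medication rule in the same section imputes stop dates to the end of the period with no treatment-stop cap, so the cap is not a needed convention.

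**Conclusion.** The rule is wrong as written, and the consequence is minor. For an AE with a partial stop date in a month after treatment ended, it yields a date the record contradicts. For an AE that began after the last dose, it yields a stop before the start. Where the recorded stop month is later than the treatment-stop month, the error is always towards earlier resolution and is at least the interval from last dose to that month, against at most 30 days without the cap.

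The effect is limited to Figures 13.0190 and 13.0191. The conclusion about what readers would see rests on two assumptions: those figures draw AE end dates, and treatment stop means last dose. How many records are affected cannot be known from the plan.

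**What to change.** In Section 16.7.2.1, under Missing Stop Day, delete the reference to the treatment stop date and replace the rule with: use the last day of the recorded month, but not later than the date of death, last contact or data cut-off, and not earlier than the AE start date. In the examples above this gives 30 September for the September stop and 30 June for the event starting on 5 April.

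The cost is one sentence in the SAP and one line of code. No table, listing, endpoint or derived duration changes.
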